13.5 Protocol Amendments

Any changes that affect patient safety or welfare will be submitted to the IRB/IEC and Regulatory Authority (where applicable) for approval prior to implementation. The Investigator and the Sponsor must approve all amendments. No amendment will be implemented until approved and signed by all parties. Exceptions to this are when the Investigator considers that the patient's safety is compromised.

Once the study has started, amendments should be made only in exceptional cases. The changes then become part of the study protocol.

13.6 IRB/IEC Approval and Reporting

The Investigator must obtain appropriate IRB approval prior to study initiation. A copy of the written approval from the IRB and a copy of the approved ICF should be sent to the Sponsor or its delegate. It is also necessary to submit a list of the IRB members (including their Institution

affiliations, gender makeup, and occupations) or supply a statement from the IRB specifying that the membership complies with applicable regulations.

The study protocol, patient information and consent form, the Investigator Brochure, available safety information, patient recruitment procedures (e.g., advertisements), information about payments and compensation available to the patients and documentation evidencing the Investigator's qualifications should be submitted to the IRB/IEC for ethical review and approval according to local regulations, prior to the study start. The written approval should identify all documents reviewed by name and version.

Any changes to the protocol must be approved by the Sponsor in writing unless the change is proposed to assure safety of the patient. In the non-emergent setting, following agreement on the proposed changes, an amendment to the protocol will be submitted by the Sponsor to the IRB for approval prior to implementation of the change. Any change made emergently must be documented in the patient's medical record.

If required by legislation or the IRB/IEC, the Investigator must submit to the IRB/IEC:

- Information on serious or unexpected AEs as soon as possible;
- Periodic reports on the progress of the study.

13.7 Closure of the Study

The Sponsor, its authorized representative, or the Investigator has the right to close this study at any time. The IRB/IEC must be informed, if required by legislation. Should the study be closed prematurely, all unused SL-401 will be reconciled with dispensing records, documented, and, if directed by the Sponsor, destroyed at the study site after completion of accountability by the site monitor.

13.8 Record Retention

The Sponsor will maintain copies of correspondences, records of shipment and disposition of study drug, adverse effects, and other records related to the clinical study and the signed Investigator agreements. Retained records will enable the tracing of patients who have participated in the study. Notes of patients who have enrolled in the study must be retained if the patient has died.

Study documents must be retained by the Investigator for a minimum of 2 years after the last approval of a marketing application in an ICH region and until there are no pending or contemplated marketing applications in an ICH region or at least 2 years have elapsed since the formal discontinuation of clinical development of the investigational product. These documents should be retained for a longer period, however, if required by the applicable regulatory requirements or by an agreement with the Sponsor. It is the responsibility of the Sponsor to

inform the Investigator when storage of these documents is no longer required. The Investigator should contact the Sponsor if the site's archiving arrangements change at any time.

13.9 Liability and Insurance

Liability and insurance provisions for this study are provided in the Investigator's contract.

13.10 Financial Disclosure

Prior to study initiation the Investigator will be asked to sign a Clinical Trial Agreement. The Investigator will be required to sign a Financial Disclosure Form in accordance with 21 Code of Federal Regulations (CFR) Part 54; Financial Disclosure by Clinical Investigators.

13.11 Study Monitoring and Auditing

All aspects of the study will be carefully monitored by the Sponsor or its designee for compliance to applicable government regulations with respect to current good clinical practice and current standard operating procedures. Monitoring functions will be performed in compliance with 21CFR§812.43(d) and 21CFR§812.46. Direct access to the on-site study documentation and medical records must be ensured.

13.11.1 Study Monitoring and Source Data Verification

The Investigator is responsible for the validity of all data collected at the site and must accept the various monitoring procedures employed by the Sponsor. The purpose of monitoring is to verify the rights and well-being of human patients are protected; that study data is accurate, complete, and verifiable with source data; that the study is conducted in compliance with the protocol, GCP and the applicable regulatory requirements.

Sites will be monitored to identify and reconcile any differences between the completed eCRFs and medical records, and review Source documents for accuracy, completeness, and legibility. The monitor will review completed data forms and study documentation for accuracy, completeness, and protocol compliance. In addition, the Sponsor will evaluate any protocol deviations and take corrective action as necessary.

The Sponsor will review significant new information, including unanticipated AEs and ensure that such information is provided to all reviewing IRBs. This information will also be provided to the FDA, other regulatory authorities, and Investigators worldwide in accordance with local regulations. The monitor's responsibilities include site visits, participation in initial study sessions, review of eCRFs, source documents and results, and ensuring clear communication between Investigators and the Sponsor.

The monitor will query any missing or spurious data with the Investigator, which should be resolved in a timely manner. A monitoring log will be maintained recording each visit, the reason for the visit, the monitor's signature, and Investigator's or designee's confirmation signature.

13.11.2 Study Documentation

The Investigator must provide the Sponsor with the following documents prior to enrollment and maintain the currency of these documents throughout the course of the study.

- Completed and signed Form 1572.
- All applicable country-specific regulatory forms.
- Current signed and dated curricula vitae for the Investigator, Sub-investigators, and other individuals having significant investigator responsibility who are listed on the Form 1572 or equivalent, or the clinical study information form.
- Copy of the current medical license of the Principal Investigator, any Sub-investigators and any other individuals having significant responsibility as listed on Form 1572.
- A financial disclosure form for the Principal Investigator and any other persons listed in Form 1572.
- Copy of the IRB/IEC approval letter for the protocol and informed consent. All
 advertising, recruitment, and other written information provided to the patient must be
 approved by the IRB/IEC. Written assurance of continuing approval (at least annually)
 as well as a copy of the annual progress report submitted to the IRB/IEC must also be
 provided to the Sponsor.
- Copy of the IRB/IEC-approved informed consent document.
- A list of the IRB/IEC members or a Federalwide Assurance number.
- Copy of the protocol sign-off page signed by the Investigator.
- Fully executed Clinical Trial Agreement including budget.
- A written document containing the name, location, certification number, and date of
 certification of each laboratory to be used for laboratory assays and those of other
 facilities conducting tests. This document should be returned along with the laboratory
 director's curriculum vitae and active medical license. List of normal laboratory values
 and units of measure for all laboratory tests required by the protocol.

The sites will also be asked to maintain a Delegation of Authority Log, pharmacy logs, temperature logs, personal patient identification log and monitoring visit logs during this study.

13.11.3 Site Audits

For the purpose of compliance with GCP and regulatory agency guidelines, it may be necessary for Sponsor authorized Quality Assurance personnel and/or authorized personnel from an

external regulatory agency to conduct an audit/inspection of an Investigational site. These site reviews may be planned or spontaneous and occur at any stage during the study. The purpose of an audit is to assess the quality of data with regard to accuracy, adequacy, and consistency, and to assure that studies are in accordance with GCP, protocol, and Regulatory Agency guidelines.

The Investigator should promptly notify the Sponsor or its authorized representative of any audits by any regulatory authorities and promptly forward copies of any audit reports received to the Sponsor or its authorized representative.

Electronic data systems will be in accordance with applicable aspects of 21 CFR Part 11, ICH Guidelines, GCP, and HIPAA.

13.12 Documentation and Use of Study Findings

13.12.1 Documentation of Study Findings

Source documentation will be maintained to document the treatment and study course of a patient and to substantiate the integrity of the study data submitted for review to regulatory agencies. Source documentation for Stemline Therapeutics, Inc., studies will include, but not be limited to, worksheets, hospital and/or clinic or office records documenting patient visits including study and other treatments or procedures, medical history and physical examination information, laboratory and special assessments results, drug accountability records, and medical consultations (as applicable).

Laboratory and diagnostic reports including but not limited to: local laboratory hematology and chemistry results, BM biopsy reports, BM aspirate reports, ECHO readings, and MUGA readings may be collected by the study monitor during the course of the study. Every effort should be made by the site to de-identify personal patient information from these reports and replaces with the patients study identification number.

13.12.2 Use of Study Findings

All information concerning the product, as well as any matter concerning the operation of the Sponsor, such as clinical indications for the drug, its formula, methods of manufacture, and other scientific data relating to it, that have been provided by the Sponsor and are unpublished, are confidential and must remain the sole property of the Sponsor. The Investigator will agree to use the information only for the purposes of carrying out this study and for no other purpose unless prior written permission from the Sponsor is obtained. The Sponsor has full ownership of the eCRFs completed as part of the study.

All publications and presentations of the results of the Study are governed by the applicable provisions of the Clinical Trial Agreement between the Sponsor and the institution. By signing the study protocol, the Investigator agrees that the results of the study may be used for the purposes of national and international registration, publication, and information for medical and pharmaceutical professionals by the Sponsor. If necessary, the authorities will be notified of the

Investigator's name, address, qualifications, and extent of involvement. The Investigator may not publish or present any information on this study without the express written approval of the Sponsor. Additionally, the Sponsor may, for any reason, withhold approval for publication or presentation. If the Investigator is to be an author of a publication manuscript prepared by the Sponsor, the Sponsor will allow the Investigator 30 days for full review of the manuscript before publication. Such manuscript or materials should be provided for Sponsor review only after the final database is available.

14 References

15.1 ECOG Performance Status

Grade	Description
0	Able to carry out all normal activities without restriction.
1	Restricted in physically strenuous activity but ambulatory and able to carry out work of a light or sedentary nature.
2	Ambulatory and capable of all self-care but unable to carry out any work activities: up and about more than 50% of waking hours.
3	Capable of limited self-care; confined to bed or chair more than 50% of waking hours.
4	Completely disabled; cannot carry on self-care; totally confined to bed or chair.

15.2 International Myeloma Working Group Response Criteria

Response	IMWG criteria
sCR	CR as defined below plus: normal FLC ratio and absence of clonal cells in bone marrow-by immunohistochemistry or 2 – 4 color flow cytometry
CR	 Negative immunofixation on the serum and urine and disappearance of any soft tissue plasmacytomas and < 5% plasma cells in bone marrow. In patients with only FLC disease, a normal FLC ratio of 0.26–1.65 is required.
VGPR	 Serum and urine M-protein detectable by immunofixation but not on electrophoresis or 90% reduction in serum M-protein plus urine M-protein level < 100 mg/24 h. In patients with only FLC disease, >90% decrease in the difference between involved and uninvolved FLC levels is required.
PR	 50% reduction of serum M-protein and reduction in 24 hours urinary M-protein by ≥90% or to < 200 mg/24 h If the serum and urine M-protein are unmeasurable, a ≥ 50% decrease in the difference between involved and uninvolved FLC levels is required in place of the M-protein criteria If serum and urine M-protein are not measurable, and serum free light assay is also not measureable, ≥ 50% reduction in plasma cells is required in place of M-protein, provided baseline bone marrow plasma cell percentage was ≥ 30% In addition to the above listed criteria, if present at baseline, a ≥ 50% reduction in the size of soft tissue plasmacytomas is also required
Minimal response in patients with RRMM adapted from the EMBT criteria	 ≥ 25% but < 49% reduction of serum M protein and reduction in 24 hour urine M protein by 50 – 89%, which still exceeds 200 mg/24hrs. In addition to above; if present at baseline, 25-49% reduction in the size of soft tissue plasmacytomas is also required No increase in size or number of lytic bone lesions (development of compression fractures does not exclude response)
Stable Disease	Not meeting criteria for CR, VGPR, PR or progressive disease

Response	IMWG criteria
Progressive	Increase of ≥ 25% from lowest response value in any 1 of the following:
disease	 Serum M-component (the absolute increase must be ≥ 0.5 g/dL)⁴ and/or
	 Urine M-component (the absolute increase must be ≥ 200 mg/24 h) and/or
	 Only in patients without measurable serum and urine M-protein, the difference between involved and uninvolved FLC levels. The absolute increase must be > 10 mg/dL
	 Only in patients without measurable serum and urine M-protein and without measurable disease by FLC levels, bone marrow plasma cell percentage (absolute % must be ≥ 10%)
	 Definite development of new bone lesions or soft tissue plasmacytomas or definite increase in the size of existing bone lesions or soft tissue plasmacytomas
	 Development of hypercalcemia (corrected serum calcium > 11.5 mg/dL) that can be attributed solely to the plasma cell proliferative disorder

All relapse categories (CR, sCR, VGPR, and progressive disease) require 2 consecutive assessments made at any time before the institution of any new therapy; complete response and PR and SD categories also require no known evidence of progressive or new bone lesions if radiographic studies were performed. VGPR and CR categories require serum and urine studies regardless of whether disease at baseline was measurable in serum, urine both or either. Radiographic studies are not required to satisfy these response requirements. Bone marrow assessments need not be confirmed. For progressive disease, serum M-component increases of ≥ 1 gm/dl are sufficient to define response if starting M-component is ≥ 5 g/dl.

IMWG clarification for coding progressive disease: Clarified that Bone marrow criteria for progressive disease are to be used only in patients without measurable disease by M protein and by FLC levels. Clarified that 25% increase refers to M protein, FLC, and bone marrow results and does not refer to bone lesions, soft tissue plasmacytomas or hypercalcemia. Note the lowest response value does not need to be a confirmed value.

FreeLite™ Disease Response Criteria

Complete Response: For those patients being followed by serum free light chain (and NO measurable serum or urine M-spike), which were immunofixation negative at enrollment, normalization of serum free light chain ratio.

Normalization is defined as the serum free light chain ratio being within the normal range. If the serum free light chain ratio is not within the normal range, but the individual kappa and lambda light chain values are within normal range, this may be considered CR.

Partial Response: If only measurable parameter is serum immunoglobulins FLC, EITHER of the following changes quality as partial response:

- A 50% decrease in the difference between involved and uninvolved FLC levels; OR
- A 50% decrease in the level of involved FLC AND a 50% decrease (or normalization) in the ratio of involved/uninvolved FLC

Progressive Disease: If only measurable parameter is serum immunoglobulins free light (FLC), either of the following qualify as progression:

- 50% increase in the difference between involved and uninvolved FLC levels from the lowest response level, which must also be an absolute increase of at least 10 mg/dL; OR
- 50% increase in the level of involved FLC AND a 50% increase in the ratio of involved/uninvolved FLC from the lowest response level.

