- Hematology: CBC to be performed and reviewed by clinician prior to SL-401 dosing on Days 1 5 and Days 8, 15 and 22 or as clinically indicated. The Run in and Cycle
 1, Day 1, results must remain within the entry criteria values to initiate therapy.
- g. Serum Chemistry: to be performed and reviewed by clinician prior to SL-401 dosing on Days 1 5 and Days 8, 15, and 22 or as clinically indicated. The Run in and Cycle 1 Day 1 results must remain within the entry criteria values to initiate therapy. Chemistry includes: glucose (fasting at baseline), albumin, total protein, AST, ALT, bilirubin

- (total and direct), alkaline phosphatase, LDH, CPK, sodium, potassium, chloride, bicarbonate/carbon dioxide, calcium, magnesium, phosphate, uric acid, BUN, serum creatinine and estimated creatinine clearance (Cockroft-Gault formula Appendix 15.7). Albumin, transaminases (AST/ALT) and creatinine must be evaluated prior to each SL-401 dose.
- Urinalysis: Appearance, color, pH, specific gravity, ketones, leukocytes, protein, glucose, bilirubin, urobilinogen, and occult blood. To be performed at baseline, during the treatment period as clinically indicated and EOT.
- i. Plasmacytoma Assessment Disease: For patient with known or suspected plasmacytomas, assess by physical exam and/or radiologic evaluation at baseline and as clinically indicated. Disease that can be assessed by physical exam should be evaluated on Day 1 of each cycle. Disease that can be assessed by radiologic evaluation should be assessed according the IMWG criteria for evaluation of response. This may include computerized tomography (CT) scan, ultrasound, PET/CT or MRI. The same method of assessment should be used at each evaluation for any individual patient. Assess the need to evaluate for suspected new, worsening, or improved plasmacytomas to confirm response or progression every cycle. Evaluations may be performed on Day 1 of a cycle or during the 7 days prior to Day 1 of the Cycle as needed for scheduling.
- j. Skeletal Survey: Plain film X-rays to including skull, vertebrae, all long bones, pelvis and chest are required. PET/CT MRI may be done to supplement X-rays of any disease site at Investigators discretion. Also required at any time when clinically indicated, for suspected progression per IMWG response criteria.

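### VGPR is the only response category in Appendix 15.2 without a plasmacytoma condition, so an unchanged baseline plasmacytoma blocks PR but not the deeper VGPR that counts in ORR

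*Protocol*

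**What the plan says.** Appendix 15.2 defines the response categories row by row.

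- CR includes "disappearance of any soft tissue plasmacytomas and < 5% plasma cells in bone marrow". sCR is CR plus further conditions, so it inherits this.
- PR: "if present at baseline, a ≥ 50% reduction in the size of soft tissue plasmacytomas is also required".
- MR: "if present at baseline, 25-49% reduction in the size of soft tissue plasmacytomas is also required".
- VGPR: the M-protein condition reads "detectable by immunofixation but not on electrophoresis or 90% reduction in serum M-protein plus urine M-protein level < 100 mg/24 h". For FLC-only disease: "In patients with only FLC disease, >90% decrease in the difference between involved and uninvolved FLC levels is required". The row does not mention plasmacytomas.

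SD is the residual category for patients who meet none of CR, VGPR, PR or progression. Progression covers new plasmacytomas and a definite increase in existing ones.

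Section 11.6 defines ORR as CR + VGPR + PR and clinical benefit rate as the same plus MR, and also reports depth of response. Table 13 note i covers plasmacytoma assessment ("Disease that can be assessed by radiologic evaluation should be assessed according the IMWG criteria for evaluation of response"), and Section 9.3.1 lists extramedullary disease evaluation where needed to confirm response.

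**The concern.** Response categories should be nested: a patient in a deeper category should meet the conditions of every shallower one. Here they are not. VGPR ranks above PR and MR, but it is the only response category with no condition on baseline plasmacytomas. A lesion that disqualifies a patient from PR does not disqualify the same patient from VGPR.

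The affected patients can enter the trial. No exclusion criterion removes patients with plasmacytomas, and Sections 8.5 and 8.10 and Table 13 provide for their assessment. Inclusion criterion 6 requires measurable serum, urine or FLC disease in everyone, so a VGPR-level serologic fall can occur alongside unresponsive extramedullary disease. ORR, clinical benefit rate and depth of response would then credit a response that the PR and MR rows deny.

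**Working it through.** The plan gives no figure to reproduce on this point. The check is a reading of the rows side by side, followed by the effect on ORR.

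**Step 1: plasmacytoma condition by category (Appendix 15.2)**

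| Category | Condition on a baseline plasmacytoma |
|---|---|
| sCR, CR | must be gone |
| VGPR | none |
| PR | at least 50% smaller |
| MR | 25-49% smaller |
| SD | residual category |
| Progression | new or definitely larger |

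**Step 2: does other text supply the missing condition?**

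- The phrase that adds the plasmacytoma condition in the PR row refers to that row's own criteria.
- The paragraph after the table adds a condition on bone lesions, not soft tissue plasmacytomas, and does not name VGPR: "complete response and PR and SD categories also require no known evidence of progressive or new bone lesions if radiographic studies were performed".
- The FreeLite criteria define CR, PR and progression, not VGPR.
- No sentence says that VGPR must also satisfy PR.

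**Step 3: apply the rows to test patients.** Each has a baseline plasmacytoma and urine M-protein of 50 mg/24 h.

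| Patient | Serum M-protein fall | Plasmacytoma shrinkage | VGPR row | PR row | MR row | In ORR? |
|---|---|---|---|---|---|---|
| A | 95% | 0% | met | not met | not met | yes, as VGPR |
| B | 60% | 0% | not met | not met | not met | no, SD |
| C | 95% | 60% | met | met | not met | yes, as VGPR |

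- A meets PR's M-protein conditions (95% is at least 50%; 50 is below 200 mg/24 h) and fails PR only on the lesion. CR fails because the lesion is still there. The lesion is unchanged, so A has not progressed. A meets VGPR, so A cannot be SD.
- B is assumed still to have M-protein visible on electrophoresis. B has the same lesion and is a non-responder.
- C shows that a patient whose lesion shrinks enough keeps VGPR if the PR condition is added.

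**Step 4: effect on ORR.** Section 11.3 gives 20 patients at the phase 2 dose, so one reclassified patient moves ORR by 1/20 = 5 points. The exact (Clopper-Pearson) 95% limits for x of n are the 0.025 quantile of Beta(x, n - x + 1) and the 0.975 quantile of Beta(x + 1, n - x).

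- 7/20 = 35%: 15.4% to 59.2%
- 8/20 = 40%: 19.1% to 63.9%

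Clinical benefit rate moves by the same 5 points, because A fails MR too.

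**Step 5: how many such patients?** The protocol does not say. As a pure assumption, if 10-20% have a baseline plasmacytoma and 10-25% of those reach a serologic VGPR without 50% shrinkage, the expected number is 20 x 0.10 x 0.10 = 0.2 to 20 x 0.20 x 0.25 = 1.0 patient, or 1 to 5 points of ORR.

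**The case against.** The strongest reply is that the table reproduces named external criteria and that ORR is defined by reference to them. Whether the missing clause is a copying slip or stands in the source cannot be told from the protocol. If it stands in the source, adding it departs from the named standard. A classifier might also treat a very good partial response as a kind of PR because of its name. Both points bear on how the fix is labelled. Neither removes the inconsistency, because the protocol's own table states no such rule.

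It is also fair that the effect is small. The cases are narrow, the frequencies in step 5 are assumed, and the two example intervals overlap almost entirely. No decision rests on ORR. The 33% ORR for POM plus DEX in Section 3.5.5 is background, not a threshold. The only hypothesis test is on PFS-6, which depends on progression and not on the VGPR row.

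Three stronger readings are tempting, and the protocol does not support them.

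- *VGPR patients with new or growing bone lesions are counted as responders.* The bone-lesion sentence omits VGPR, but new or definitely enlarging bone lesions are already progression. Adding VGPR there would change no classification.
- *CR and PR can be assigned without checking the plasmacytoma.* The appendix says "Radiographic studies are not required to satisfy these response requirements", but the paragraph's only earlier mention of radiography concerns bone lesions. The CR and PR rows keep their shrinkage conditions, and Table 13 note i requires the same assessment method throughout and a check every cycle of whether plasmacytomas need evaluation. The sentence is loose; it is not a waiver.
- *DOR is biased upward.* The set of responders changes, but a patient with unresponsive extramedullary disease could progress early or late. No direction is shown.

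**Conclusion.** The point holds in a narrow form. Followed as written, Appendix 15.2 classes as VGPR a patient whose M-protein or FLC falls to VGPR level while a baseline plasmacytoma has neither shrunk by 50% nor grown. That patient fails PR. The error runs one way for ORR and clinical benefit rate: each case adds 5 points when 20 patients are analysed, and the patient also enters depth of response in a deeper category than the one denied.

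The existence of the gap rests only on the wording of the table. Its size rests on an unknown number of such patients; under the assumptions above it is at most about one in 20. The endpoints are secondary and descriptive, and the PFS-6 test is untouched. It is a modest defect, but worth correcting because the rule gives a wrong classification and the remedy is nearly free.

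**What to change.** Add one condition to the VGPR row of Appendix 15.2, covering both the M-protein and the FLC-only definitions: where soft tissue plasmacytomas were present at baseline, the PR requirement of at least a 50% reduction in their size must also be met. Refer to Table 13 note i and Section 9.3.1 for how and when the lesions are assessed. If the source criteria lack this condition, say in the appendix that it is a study-specific clarification.

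The cost is a wording change in one appendix, with no assessment beyond those already provided for. ORR may come out slightly lower. The change is best made before responses are classified, since the study is open-label and deciding individual cases afterwards would be harder to defend. The bone-lesion sentence needs no edit for this purpose.
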